3.6.9 Vital signs

3.6.10 Fluid intake and urine output (I/O)

3.6.11 Weight

3.6.12 Interval history and physical examination

**3.7 MONITORING DURING FOLLOW-UP PERIOD (AFTER COMPLETION OF TREATMENT)**

The following tests and procedures will be performed during the follow-up portion of the study, as indicated in Section **3.8**, Study Calendars.

3.7.1 Vital signs

3.7.2 Weight

3.7.3 History and physical examination, including documentation of performance status

3.7.4 ANA, RF, anti-thyroid antibody and thyroid function tests: TSH and T4

3.7.5 Acute Care, Hepatic and Mineral Panels and LDH

3.7.6 CBC with differential

3.7.7 Radiographic evaluation and laboratory assessments for clinical responses

### 3.8 STUDY CALENDARS

#### 3.8.1 10 Day Schedule

Procedure	Pre-treatment		Day on Treatment (For All Cycles  )											During-treatment			Follow-Up Period 	End of Study 
	Screening	Baseline 	1	2	3	4	5	6	7	8	9	10	11	12 	21-27	28-34		
CIV rhIL-15 treatment 			x	x	x	x	x	x	x	x	x	x	x					
Pathology confirmed	x																	
Performance status	x	x	x						x							x	x	x
History & physical exam 	x	x	x	x	x	x	x	x	x	x	x	x	x		x	x	x	
Vital Signs  and Weight	x	x	x	x	x	x	x	x	x	x	x	x	x		x	x	x	
Acute Care, Hepatic and Mineral Panels and LDH	x			x	x	x	x	x	x	x	x	x	x		x	x	x	
Ammonia level	x			x										x				
I/Os				x	x	x	x	x	x	x	x	x	x	x	x	x		
CBC w/differential,	x	x	x	x	x	x	x	x	x	x	x	x	x	x	x	x	x	x
Reticulocyte Count		x																
Hepatitis and HIV serology	x																	
Thyroid function panel	x															x		
Troponin T		x	x				x							x		x		
Urinalysis	x																	
EKG	x		x									x			x			
Pulmonary function tests	x																	
HLA (A, B, C, DR, DQ) typing		x																
Tumor imaging and serum tumor markers 	x	x													x 	x		
Serum $\beta$ HCG 	x		x															
ANA, RF and anti-thyroid antibodies	x															x		
Pharmacokinetics (PK) 			x	x	x			x	x	x	x	x	x					
Serum immunoglobulin levels		x																
Flow cytometry ([name] Lab) 		x	x					x				x		x	x	x		
Flow cytometry ([name] Lab) 		x	x					x				x		x	x	x		
Cytokine and MesoScale inflammatory cytokines 			x	x				x				x						
Anti-IL-15 antibodies 			x									x		x	x	x	x	
Optional Tumor Biopsy 		x										x						

1. Cycles 1 and 2 for the 10-day dosing schedule will be 42 days in length, but subsequent cycles will be 28 days in length with all cycles allowing an additional 7 days allowed for reasons other than recovery for treatment-related toxicities.
2. Day 12 tests and procedures only occur on Cycle 1.
3. Patients whose best response after 2 consecutive cycles of treatment is stable disease will be followed with routine exams and restaging scans: Every 60 days x 3; then quarterly for up to 2 years after starting treatment unless progressive disease is documented, or they begin another treatment for their cancer.
4. Denotes testing to be performed at an end of study visit (just prior to the patient being taken off study), if feasible.
5. Because the treatment is CIV for 240 hours, the day 10 treatment concludes on day 11.
6. Interval history during inpatient treatment period.
7. Vital signs, including heart rate, blood pressure, respiration, temperature and arterial oxygen saturation (SO2) by transcutaneous pulse-oximeter.
  - a. Every 4 hours during treatment days 1 through 11 (SO2 every 8 hours)
  - b. Every 8 hours on other inpatient days
  - c. Once at outpatient clinic follow-up visits on day 28.
  - d. Off treatment visit
  - e. End of study visit.
8. Repeat radiologic studies to assess response week 4 of cycles 1 and 2. Subjects that go onto to receive additional cycles of treatment will have restaging after every other cycles (4, 6, 8 etc.) and may be restaged earlier if the subject has complaints or findings that indicate progressive disease. Subjects with evidence of a partial or complete response (RECIST criteria) may undergo a confirmatory scan at least 4 weeks after the scan which first met the criteria for a clinical response. Patients with tumors known to have tumor markers (PSA, CEA, and CA125) will have the serum level of these markers assessed at the time of their radiographic restaging.
9. Pretreatment on Day 1 or within 3 days of starting treatment in women of child bearing potential.
10. PKs are collected on Cycle 1 only. Samples are collected in 4 mL SST tubes at the time points listed in Section [5.1.1](#). These samples will be held at room temperature until picked up by the [name] laboratory for processing ([contact] for pickup). See Section [5.1](#) for additional details.
11. One 10 mL lavender-top tube will be drawn for Lymphocyte Phenotype IL-15 FACS analysis. If the Immunology Section Laboratory is unable to perform this analysis on the specified days, this assessment maybe omitted or replaced with standard TBNK panel. See Section [5.1.2](#) for additional details:
  - a. At baseline (need to perform twice before initiating study drug if at all possible.)
  - b. Day 1: prior to the start of the CIV rhIL-15 infusion
  - c. Days 8 and 12 drawn with the routine AM laboratories
  - d. Days 21and 28: at the same time as the outpatient blood draws.
12. Two 10 mL lavender-top tubes will be drawn for the [name] Lab (NIAID) to perform special FACS analysis. See Section [5.1.2](#) for additional details:
  - a. At baseline (OK to draw on Day 1 or up to 2 weeks prior to initiating study drug.)
  - b. Day 2: 24 hours after starting the CIV rhIL-15 infusion
  - c. Days 8 and 12: Samples may be drawn with the routine AM laboratories
  - d. Days 21and 28: Samples may be drawn at the same time as the outpatient blood draws.
13. Cytokine and MesoScale inflammatory cytokines are collected on cycle 1 only: Samples to assess for IL-2R $\alpha$  IL-18, MIP2, MIP1 $\alpha$ , TNF $\alpha$  and MesoScale Discovery Multiplex Pro-Inflammatory Cytokines (IL-1 $\beta$ , IL-12p70, Interferon  $\gamma$ , IL-6, IL-8 and IL-10) will be obtained from the same SST tubes drawn for PK time points drawn at the time listed above in # 10. See Section [5.1.3](#) for additional details.
14. For all samples: Assessments that fall on a Friday, Saturday or Sunday due to an individual patient's treatment schedule will be shifted forward or backward to the nearest day that these laboratories are able to process the time sample.
15. Optional biopsies will be performed (if patient agrees) pre-treatment and one subsequent time between Day 8 and Day 21 as determined by clinical response and/or changes in lymphocyte subsets.
16. If baseline tests were already performed and meet the required time frames, they will not need to be repeated.

### 3.8.2 5 Day Schedule

Procedure	Pre-treatment		Days During-treatment 							After treatment			
	Screening	Baseline 	1	2	3	4	5	6	8	21±4 	End of Treatment 	Follow-Up Period 	End of Study 
CIV rhIL-15 treatment 			x	x	x	x	x	x 					
Pathology confirmed	x												
Performance status	x	x	x						x		x	x	x
History & physical exam 	x	x	x	x	x	x	x	x	x		x	x	x
Vital Signs  and Weight	x	x	x	x	x	x	x	x	x		x	x	x
NIH Advance Directives Form 													
Acute Care, Hepatic and Mineral Panels and LDH	x	x	x	x	x	x	x	x	x	x	x	x	x
Ammonia level	x		x						x				
I/Os			x	x	x	x	x	x	x				
CBC w/differential	x	x	x	x	x	x	x	x	x	x	x	x	x
Reticulocyte Count		x											
Hepatitis and HIV serology	x												
Thyroid function tests: TSH and T4	x									x	x		
Troponin T or I, based on availability of test in DLM		x	x										
Urinalysis	x												
EKG	x		x										
Pulmonary function tests	x												
HLA (A, B, C, DR, DQ) typing		x											
Tumor imaging and serum tumor markers 	x	x									x		
Serum βHCG 	x		x										
ANA, RF and anti-thyroid antibodies	x										x		
Pharmacokinetics (PK) 			x	x	x	x	x	x					
Serum immunoglobulin levels		x											
Flow cytometry ([name] Lab) 		x	x						x	x			
Flow cytometry ([name] Lab) 		x	x						x	x			
Cytokine and MesoScale inflammatory cytokines 			x	x	x	x	x	x	x	x			
Anti-IL-15 antibodies 			x							x		x	
Optional Tumor Biopsies 		x							x				

**Abbreviated Title:** Ph I Study of CIV rhIL-15

**Version Date:** 06/13/2018

1. All cycles are 21 days in length, but the end of cycle evaluations may be performed  $\pm$  4 days from this time point and an additional 7 days allowed for reasons other than recovery for treatment-related toxicities. Cycle 1 day 21 and cycle 2 day 1 maybe the same calendar day for certain patients. This also applies to later cycles where day 21 of a previous cycle falls on the same calendar day as day 1 of the subsequent cycle.
2. Patients whose best response after 4 consecutive cycles of treatment is stable disease will be followed with routine exams and restaging scans: Every 60 days x 3; then quarterly for up to 2 years after starting treatment unless progressive disease is documented, or they begin another treatment for their cancer.
3. Denotes testing to be performed at an end of study visit (just prior to the patient being taken off study), if feasible.
4. Because the treatment is CIV for 120 hours, the day 5 treatment concludes on day 6.
5. Interval history during inpatient treatment period.
6. Vital signs, including heart rate, blood pressure, respiration, temperature and arterial oxygen saturation (SO2) by transcutaneous pulse oximeter.
  - a. Every 4 hours  $\pm$  1 hour during treatment days 1 through 6 (SO2 every 8 hours  $\pm$  1 hour)
  - b. Every 8 hours  $\pm$  1 hour on other inpatient days
  - c. Once at outpatient clinic follow-up visits on days 8 and 21.
  - d. Off treatment visit
  - e. End of study visit.
7. Repeat radiologic studies to assess response the last week (day 14 through 21) of even numbered cycles (2, 4, 6 and so on) as long as patients meet criteria to continue treatment. Patients with evidence of a partial or complete response (RECIST criteria) may undergo a confirmatory scan at least 4 weeks after the scan which first met the criteria for a clinical response. Patients with tumors known to have tumor markers (PSA, CEA, and CA125) will have the serum level of these markers assessed at the time of their radiographic restaging.
8. Pretreatment on Day 1 or within 3 days of starting treatment in women of child bearing potential.
9. PKs are collected on Cycle 1 only. Samples are collected in 4 mL SST tubes at the time points. These samples will be held at room temperature until picked up by the [name] laboratory (Blood Processing Core) for processing ([contact] for pickup). See Section [5.1](#) for additional details.
10. One 10 mL lavender-top tube will be drawn for Lymphocyte Phenotype IL-15 FACS analysis. If the Immunology Section Laboratory is unable to perform this analysis on the specified days, this assessment maybe omitted or replaced with standard TBNK panel. See Section [5.1.2](#) for additional details:
  - a. At baseline (need to perform twice before initiating study drug if at all possible.)
  - b. Day 1: prior to the start of the CIV rhIL-15 infusion
  - c. Days 8 and 21 drawn with the routine laboratories
11. Two 10 mL lavender-top tubes will be drawn for the [name] Lab (NIAID) to perform special FACS analysis. See Section [5.1.2](#) for additional details:
  - a. At baseline (need to perform twice before initiating study drug if at all possible.)
  - b. Day 1: prior to the start of the CIV rhIL-15 infusion
  - c. Days 8 and 21 drawn with the routine laboratories
12. **Cytokine and MesoScale inflammatory cytokines are collected on cycle 1 only:** Samples to assess for IL-2R $\alpha$  IL-18, MIP2, MIP1 $\alpha$ , TNF $\alpha$  and MesoScale Discovery Multiplex Pro-inflammatory Cytokines (IL-1 $\beta$ , IL-12p70, Interferon  $\gamma$ , IL-6, IL-8 and IL-10) will be obtained from the same SST tubes drawn for PK time points drawn at the time listed in Section [5.1.3](#). Refer to this Section for additional details.
13. For all samples: Assessments that fall on a Friday, Saturday or Sunday due to an individual patient's treatment schedule will be shifted forward or backward to the nearest day that these laboratories are able to process the time sample.
14. Optional biopsies will be performed (if patient agrees) pre-treatment and one subsequent time between Day 8 and Day 21 as determined by clinical response and/or changes in lymphocyte subsets.
15. If baseline tests were already performed and meet the required time frames, they will not need to be repeated.
16. End of treatment visit will occur approximately 30 days after the last dose of study drug. If the patient cannot return to the Clinical Center, a request will be made to collect clinical labs from a local physician or laboratory. If this is not possible, patients may be assessed by telephone for symptoms.
17. All subjects will be offered the opportunity to complete an NIH advance directives form (Section [10.3](#)); preferably done at baseline, but can be done at any time during the study as long as the capacity to do so is retained. The completion of the form is strongly recommended, but is not required.

### **3.9 CONCURRENT THERAPY**

Concurrent anti-cancer therapy to include immunotherapy, immunosuppressive therapy, radiation therapy or chemotherapy, and administration of systemic corticosteroids except for physiologic replacement doses of cortisone acetate is not permitted while on the study. Initiation of medically indicated, non-oncologic medications such as anti-hypertensive agents or antibiotics for urinary tract infections that do not have significant potential for interaction with the rhIL-15 treatment are allowable with prior approval of the PI.

### **3.10 CRITERIA FOR REMOVAL FROM THE PROTOCOL THERAPY AND OFF-STUDY CRITERIA**

Prior to documenting removal from study, effort must be made to have all subjects complete a safety visit approximately 30 days following the last dose of study therapy.

#### **3.10.1 Off-Treatment Criteria**

- DLT as defined in Section [3.2](#).
- Persistent (> 14 days) treatment-related grade 2 (non-DLT) adverse events.
- Completion of protocol therapy
- Patient requests to be withdrawn from active therapy.
- Disease progression.
- No evidence of clinical response (i.e., patient has stable disease) on radiographic restaging after 2 consecutive cycles of treatment.
- The detection of anti-IL-15 neutralizing antibody serum titer  $\geq 500$  ng/mL as described in [APPENDIX C](#) prior to subsequent treatment cycles.
- Evidence the patient has developed auto-immunity that involves a vital organ (heart, kidney, brain, eye, thyroid or adrenal gland, colon, lung). Patients who develop new auto-antibodies without clinical evidence of end organ dysfunction will be seen by the appropriate Internal Medicine subspecialists to assess their risk for developing an autoimmune syndrome.
- Interruption of CIV rhIL-15 treatment for any reason for more than 24 consecutive hours during cycle 1. Stoppage of less than 15 minutes occurring during the daily change of the rhIL-15 infusion device will not be considered an interruption.
- Positive pregnancy test

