Patients receiving the 10-day treatment schedule without evidence of an ongoing response after any 2 consecutive cycles of treatment will discontinue rhIL-15 and be followed until disease progression is documented or they go off study for another reason. (Ongoing response is defined as: > 15% decrease in sum of marker lesions and/or improvement or disappearance of some non-measurable lesions and/or > 10% decrease in tumor markers.) Patients receiving the 5-day treatment schedule will have 4 cycles of treatment to demonstrate responsiveness to rhIL-15, so that patients are given an equal number of rhIL-15 doses to confirm the treatment has sufficient activity to justify more prolonged treatment.

Patients who demonstrate a complete response (CR) to treatment will receive 2 additional cycles after the cycle where the CR is first documented.

Patients whose best response after 2 consecutive cycles of treatment is stable disease and those who stop treatment due to toxicity will be followed with routine exams and restaging x-rays (every 60 days x 3 and then quarterly) unless progressive disease is documented or they begin another treatment for their cancer.

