#### 6.2.2.4 Evaluation of Target Lesions

**Complete Response (CR):** Disappearance of all target lesions. Any pathological lymph nodes (whether target or non-target) must have reduction in short axis to <10 mm.

**Partial Response (PR):** At least a 30% decrease in the sum of the diameters of target lesions, taking as reference the baseline sum diameters.

**Progressive Disease (PD):** At least a 20% increase in the sum of the diameters of target lesions, taking as reference the smallest sum on study (this includes the baseline sum if that is the smallest on study). In addition to the relative increase of 20%, the sum must also demonstrate an absolute increase of at least 5 mm. (Note: the appearance of one or more

new lesions is also considered progressions).

**Stable Disease (SD):** Neither sufficient shrinkage to qualify for PR nor sufficient increase to qualify for PD, taking as reference the smallest sum diameters while on study.

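### Four rules conflict or cannot be applied as written, chiefly stopping for stable disease after 2 cycles when the 5-day schedule is promised 4

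*Combined protocol and SAP*

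**What the plan says.** **Stopping for stable disease.** Section 3.10.1 takes a patient off treatment for "No evidence of clinical response (i.e., patient has stable disease) on radiographic restaging after 2 consecutive cycles of treatment". It names no schedule. Section 3.1 says "Patients receiving the 5-day treatment schedule will have 4 cycles of treatment to demonstrate responsiveness to rhIL-15" and gives the reason: "so that patients are given an equal number of rhIL-15 doses to confirm the treatment has sufficient activity". The calendars split the follow-up rule by schedule. Section 3.8.1, footnote 3, has "Patients whose best response after 2 consecutive cycles of treatment is stable disease will be followed with routine exams and restaging scans", and Section 3.8.2, footnote 2, has "Patients whose best response after 4 consecutive cycles of treatment is stable disease will be followed". The last paragraph of Section 3.1 returns to 2 cycles without naming a schedule: "Patients whose best response after 2 consecutive cycles of treatment is stable disease and those who stop treatment due to toxicity will be followed".

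**What counts as response.** Section 3.1 states: "Ongoing response is defined as: > 15% decrease in sum of marker lesions", with improvement in non-measurable lesions or a fall in tumor markers as alternatives. Section 6.2.2.4 puts partial response at a decrease of at least 30% and defines stable disease as "Neither sufficient shrinkage to qualify for PR nor sufficient increase to qualify for PD".

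**Scans.** The first bullet of Section 6.2.1 has every patient scanned on day 28, plus or minus 3 days, of each cycle. Section 3.8.2 (footnote 7) puts 5-day scans on days 14 to 21 of even-numbered cycles. Section 3.8.1 (footnote 8) puts 10-day scans in week 4 of cycles 1 and 2, then at cycles 4, 6, 8 and so on.

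**Time to progression (TTP).** Section 6.2.4, the only definition, starts the clock at consent. It joins death and progressive disease with the word 'of', so the end event reads as death from the disease.

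**Accrual.** The second Schema footnote allows expansion to nine patients on the 5-day schedule only after at least one confirmed partial or complete response, and otherwise rules it out. Section 8 gives a minimum of 41 evaluable patients, counting 9 at dose level (DL) 9. Section 3.1 gives 41 to 47 in total and 17 to 23 still to enroll.

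**The concern.** Each pair of statements leads to different conduct or a different result, and for three of the four pairs no text says which one governs.

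- **Stopping.** Following Section 3.10.1 as written halves the exposure on which a 5-day patient is judged and defeats the equal-dose reason in Section 3.1. On either schedule, a patient with moderate shrinkage could be continued by one investigator and removed by another, each able to cite the protocol.
- **Scans.** The bullet in Section 6.2.1 calls for imaging after a 21-day cycle has ended, and in cycles where the calendars have none.
- **TTP.** A stated secondary endpoint has no settled end event. It could be death from disease, progression, or progression or death.
- **Accrual.** The minimum is too high on a branch that the protocol itself provides for: no confirmed response on the 5-day schedule.

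**Working it through.** **1. Stopping**

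Infusion days before a patient with stable disease is stopped:

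- 10-day schedule, 2 cycles: 2 × 10 = 20
- 5-day schedule, 4 cycles (Section 3.1): 4 × 5 = 20
- 5-day schedule, 2 cycles (Section 3.10.1): 2 × 5 = 10

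The equal-dose reason in Section 3.1 is correct at 4 cycles, and Section 3.10.1 gives half of that.

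For the meaning of response, take an illustrative sum of marker lesions falling from 100 mm to 80 mm: (100 − 80)/100 = 20%. This exceeds 15%, so Section 3.1 counts it as ongoing response. It is below 30%, so Section 6.2.2.4 calls it stable disease and Section 3.10.1 stops treatment after 2 cycles. The same holds for any decrease above 15% and below 30%.

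**2. Scans**

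- Section 6.2.1 window: 28 − 3 = 25 to 28 + 3 = 31.
- 5-day calendar window: days 14 to 21, so there is no overlap. The cycle ends on day 21, or on day 28 if the optional 7 extra days are used (21 + 7).
- 10-day schedule, cycles 1 and 2: Section 3.1 gives days 26 to 35, which largely agrees.
- 10-day schedule, cycle 3 onward (28 days): days 29 to 31, 3 of the 7 window days, fall after the cycle.
- Scans over four cycles: 4 under Section 6.2.1; 2 on the 5-day calendar (cycles 2 and 4); 3 on the 10-day calendar (cycles 1, 2 and 4).

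**3. TTP**

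The dates below are invented for illustration and counted from consent.

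| Course | Death from disease | Progression only | Progression or death |
|---|---|---|---|
| Progression day 42, death from disease day 120 | Event, day 120 | Event, day 42 | Event, day 42 |
| Death on day 60 from another cause, no progression | No event | No event | Event, day 60 |

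Under Section 3.1, 10-day patients without an ongoing response are followed until progression or until they leave the study for another reason. Once progression is documented, a later death from disease need not be captured.

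**4. Minimum accrual**

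Inputs from Section 8: 24 evaluable patients enrolled on DL 1 to 6, 2 more due at DL 6, minimum cohorts of 3 at DL 7 and 3 at DL 8, 9 at DL 9, and 5 inevaluable.

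The plan's own figures reproduce:

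- Minimum: 24 + 2 + 3 + 3 + 9 = 41; with inevaluable, 41 + 5 = 46
- Maximum: 24 + 2 + 6 + 6 + 9 = 47; with inevaluable, 47 + 5 = 52
- Still to enroll: 41 − 24 = 17 and 47 − 24 = 23

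With all dose levels evaluated and no confirmed response, the Schema removes the expansion:

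- 3 at DL 9: 24 + 2 + 3 + 3 + 3 = 35; with inevaluable, 40
- 6 at DL 9: 24 + 2 + 3 + 3 + 6 = 38; with inevaluable, 43
- DL 8 as the MTD, filled to 6, and 3 at DL 9: 24 + 2 + 3 + 6 + 3 = 38
- Still to enroll, lower end: 35 − 24 = 11 or 38 − 24 = 14, in place of 17

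The chance of no response among n patients with true response rate p is (1 − p)^n. Three 5-day levels of 3 to 6 patients give n = 9 to 18. The protocol states no rate, so p is assumed:

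| Assumed p | n = 9 | n = 18 |
|---|---|---|
| 5% | 0.63 | 0.40 |
| 10% | 0.39 | 0.15 |
| 20% | 0.13 | 0.02 |

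The completed IV bolus trial (Section 1.2.1.4) had no responses in 18 subjects. The exact two-sided 95% upper limit is 1 − 0.025^(1/18) = 18.5%.

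**The case against.** The strongest reply is that most of this is leftover text whose intent can be recovered.

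- **Stopping.** Section 3.1 is schedule-specific and gives its reason, and the 5-day calendar repeats 4 cycles, so Section 3.10.1 looks like a general bullet that was not updated. It also does not cite RECIST, so clinical response could mean the ongoing response of Section 3.1. This is plausible, but Section 3.10.1 is the operative list, it spells out stable disease in its own parenthesis, and the follow-up paragraph of Section 3.1 also says 2 cycles. The conflict stands.
- **Scans.** Section 3.6 refers to the calendars in Section 3.8, and Section 3.1 gives schedule-specific restaging. This largely settles the timing. What remains is one bullet in Section 6.2.1.
- **TTP.** The likeliest explanation is 'of' typed for 'or'. The literal reading contradicts the endpoint's name, the progression-only reading comes from the name and not from the definition, and death is itself an off-study reason, so some deaths would be recorded. Section 8 also calls all secondary endpoints exploratory. All of this limits the weight, but the likely correction yields progression-free survival under another name.
- **Accrual.** The sum is right on its stated components, and the wording in Sections 3.1, 3.3 and 8 is partly permissive. No test or ceiling depends on the minimum. Section 8 nevertheless presents 41 as the number required and also plans 3 to 6 further patients with no response condition. The bolus trial used another schedule and only melanoma and renal cell cancer, so it is weak evidence about the 5-day response rate. The inconsistency does not depend on that rate.

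**Conclusion.** The point holds and should be fixed, mainly for stopping, TTP and the minimum accrual; scan timing is the least of the four. The DLT, MTD and escalation rules are untouched, the response categories are well defined, and the ceilings of 47 evaluable and 52 total stand.

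The size is 10 against 20 infusion days for a 5-day patient with stable disease, opposite decisions for shrinkage between 15% and 30%, and a minimum overstated by 3 to 6 patients (41 against 38 or 35) if no 5-day response is confirmed. Those minimums assume that the Schema condition governs and that all dose levels are evaluated. Which end applies depends on whether 3 or 6 patients are needed at DL 9 without expansion, since Section 3.3 requires at least 6 at a recommended phase 2 dose. The effect on TTP cannot be sized from the documents; the dates used above are only illustrative.

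**What to change.** 1. **Stopping.** Reconcile Section 3.10.1, Section 3.1 (including its follow-up paragraph) and the footnotes in 3.8.1 and 3.8.2, so that each schedule has one removal rule and one meaning of non-response. No view is taken here on which rule is right.
2. **Scans.** Reconcile the first bullet of Section 6.2.1 with the calendars. As Section 3.6 already defers to them, a cross-reference to 3.8.1 and 3.8.2 in place of the fixed day would be enough.
3. **TTP.** Give Section 6.2.4 one end event. Either use documented progression by the solid-tumor or lymphoma criteria and state how deaths without progression are handled, or count death and rename the endpoint progression-free survival. Starting at consent is a stated choice; moving to start of treatment, as Section 6.2.2.7 does for stable disease, is optional.
4. **Accrual.** State whether the Schema's response condition applies to Sections 3.1, 3.3 and 8. If it does, restate the minimum as 35 or 38 evaluable (40 or 43 with 5 inevaluable), according to the number needed at DL 9, and the lower end of the additional enrollment as 11 or 14. If it does not, remove it from the Schema.

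The cost is text edits with no added patients. Item 1 also needs a decision, because it sets exposure for 5-day patients with stable disease. Item 3 means applying the chosen end event to dates already recorded.

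### Section 3.10.1 stops stable-disease patients after 2 cycles on either schedule, although Section 3.1 and the 5-day calendar give 5-day patients 4 cycles

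*Combined protocol and SAP*

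**What the plan says.** The off-treatment list in Section 3.10.1 includes "No evidence of clinical response (i.e., patient has stable disease) on radiographic restaging after 2 consecutive cycles of treatment". Nothing in Section 3.10 limits this to one schedule.

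Section 3.1 treats the schedules separately. On the 10-day schedule, a patient without an ongoing response after any two cycles in a row stops. For the other schedule it says "Patients receiving the 5-day treatment schedule will have 4 cycles of treatment to demonstrate responsiveness to rhIL-15", and explains that both groups should receive the same number of doses before activity is judged. The 5-day calendar (Section 3.8.2, footnote 2) agrees: "Patients whose best response after 4 consecutive cycles of treatment is stable disease will be followed with routine exams and restaging scans". The 10-day calendar (Section 3.8.1, footnote 3) has the matching sentence with 2 cycles: "Patients whose best response after 2 consecutive cycles of treatment is stable disease will be followed with routine exams and restaging scans".

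The last paragraph of Section 3.1, on follow-up, returns to a single count with no schedule named: "Patients whose best response after 2 consecutive cycles of treatment is stable disease and those who stop treatment due to toxicity will be followed".

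On timing of scans, footnote 7 of the 5-day calendar reads "Repeat radiologic studies to assess response the last week (day 14 through 21) of even numbered cycles".

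**The concern.** A 5-day patient with stable disease at the cycle-2 scan must stop under Section 3.10.1, yet is allowed two more cycles under Section 3.1 and the 5-day calendar. Section 3.10.1 is where staff would look for removal criteria, so a literal application is plausible. Either choice departs from some part of the approved text, and Sections 7.1.8 and 7.2.1 make departures reportable.

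At stake is half of the treatment a stable 5-day patient is meant to receive before activity is judged. With it go the on-treatment opportunities for a response in cycles 3 and 4, which feed the response rate and time to progression. The Schema also makes the nine-patient 5-day expansion depend on at least one confirmed response in those cohorts, although other sections do not.

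**Working it through.** **Inputs.** Infusion length is 10 days (240 hours) or 5 days (120 hours) per cycle (Section 3.4). The cycle counts come from Sections 3.1, 3.8.1, 3.8.2 and 3.10.1. The 5-day cycles last 21 days (Section 3.1), with dose levels of 3, 4 and 5 mcg/kg/day (Schema).

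**1. The plan's own parity.** Infusion days = cycles × days per cycle.
- 10-day schedule: 2 × 10 = 20.
- 5-day schedule under Section 3.1 and the calendar: 4 × 5 = 20.

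The equality claimed in Section 3.1 reproduces in infusion days. It is not an equality in mcg/kg: at the 10-day MTD of 2 mcg/kg/day, two cycles give 2 × 20 = 40 mcg/kg.

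**2. The same quantity under Section 3.10.1.** 5-day schedule: 2 × 5 = 10 infusion days, half of 20.

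**3. Can the 2-cycle criterion be met?** Yes, because a scan falls at cycle 2. Ignoring the scheduling allowances:
- Cycle 2 scan: 21 + 14 = 35 to 21 + 21 = 42, so study days 35 to 42.
- Cycle 4 scan: 63 + 14 = 77 to 63 + 21 = 84, so study days 77 to 84.

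**4. Cumulative dose before the decision.** Dose = daily dose × infusion days.

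| Dose level (mcg/kg/day) | Stop after 2 cycles (10 days) | Stop after 4 cycles (20 days) |
|---|---|---|
| 3 | 30 mcg/kg | 60 mcg/kg |
| 4 | 40 mcg/kg | 80 mcg/kg |
| 5 | 50 mcg/kg | 100 mcg/kg |

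**5. The texts side by side.**

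| Place | Schedule named | Cycles |
|---|---|---|
| 3.10.1, removal | none | 2 |
| 3.1, response rule | 10-day | 2 |
| 3.1, response rule | 5-day | 4 |
| 3.1, last paragraph (follow-up) | none | 2 |
| 3.8.1, footnote 3 (follow-up) | 10-day | 2 |
| 3.8.2, footnote 2 (follow-up) | 5-day | 4 |

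Every sentence that names a schedule, or stands in a schedule's calendar, is consistent. The two that name none give 2 cycles, which is wrong for the 5-day cohorts.

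**6. The threshold.** Section 3.1 says "Ongoing response is defined as: > 15% decrease in sum of marker lesions and/or improvement or disappearance of some non-measurable lesions", and adds a tumor-marker fall. Section 3.10.1 instead speaks of stable disease, which Section 6.2.2.4 defines for solid tumors as "Neither sufficient shrinkage to qualify for PR nor sufficient increase to qualify for PD", with PR at a 30% decrease. A patient whose sum falls by more than 15% but less than 30% therefore continues under 3.1 and stops under 3.10.1. Section 3.1 sets no separate threshold for 5-day responsiveness; the definition just before it is the likely reading.

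**7. The expansion.** The Schema expands a 5-day dose to nine patients only after at least one confirmed response. Section 3.3 allows up to nine at 5 mcg/kg/day if no MTD is found, with no response condition. Section 8 also states none, and its minimum of 24 + 2 + 3 + 3 + 9 = 41 already counts nine at the top level.

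**The case against.** The strongest reply is that the intent is clear. Section 3.1 names the 5-day schedule, gives 4 cycles and states the reason, and the 5-day calendar repeats the number. Specific text would normally prevail over a general bullet. This is a single-institution trial whose team discusses each patient weekly (Section 7.4.1), so wrongful removal at cycle 2 is possible but not shown to be likely. That stands, and it makes this a correction of wording and not a dispute about the design. It does not make the bullet right, because no section reviewed says which text prevails. Part of the repeat-cycle rationale in Section 1.2.1.6 was not available, so a statement of precedence there cannot be excluded; the operative sections would still disagree on their face.

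A second reply is that little depends on it. DLT and the MTD use cycle 1 only, Section 8 calls the secondary evaluations exploratory, and stable patients who stop are still scanned every 60 days three times and then quarterly, so a late response can be seen. This also stands and limits the importance of the point.

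A third reply is that the unqualified sentence ending Section 3.1 governs follow-up, not removal. That is correct. It still needs the cycle count by schedule, because as it stands it echoes the 2-cycle rule.

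**Conclusion.** The criterion in Section 3.10.1 is wrong as written. Followed literally, it stops a stable 5-day patient after 10 infusion days instead of the intended 20, halving the cumulative dose before the response decision at every 5-day dose level. This rests only on the protocol's cycle counts, infusion lengths and scan times. The consequences are for patients' planned treatment and the exploratory activity endpoints; cycle-1 DLT and the MTD are untouched.

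Three stronger readings go beyond the documents:

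- **A reader might infer a calculable loss in the chance of expansion.** The documents give no response rates for cycles 3 and 4, and the response condition appears in the Schema but not in Section 3.3 or Section 8. An effect on expansion exists only if the Schema governs, and no probability should be attached to it.
- **A reader might infer that all remaining 5-day patients lose half their treatment.** Section 8 implies 3 + 3 + 9 = 15 to 6 + 6 + 9 = 21 evaluable 5-day patients, but that range assumes nine at the top level. It rests on an April 2016 count in a version dated 06/13/2018, and the number already treated is not stated. The bullet bites only on those stable at the cycle-2 scan, and only if staff apply it.
- **A reader might infer a substantial 10-day problem from the difference in threshold.** On the same April 2016 count, at most 2 evaluable 10-day patients remained to be enrolled.

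**What to change.** Three edits resolve it:

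1. Reword the Section 3.10.1 bullet along these lines: *No evidence of ongoing response, as defined in Section 3.1, at radiographic restaging after any 2 consecutive cycles (10-day schedule) or after 4 cycles (5-day schedule).* This keeps the rolling rule that 3.1 sets for the 10-day schedule and replaces the stable-disease wording with 3.1's definition.
2. Add to Section 3.1 that the same definition of ongoing response applies to the 5-day schedule, and which interval applies after cycle 4. Section 3.1 is silent on that interval. The scans at even-numbered cycles can support an interval of two or four cycles; the choice is the sponsor's.
3. In the last paragraph of Section 3.1, give the cycle count by schedule: 2 for 10-day, 4 for 5-day.

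The cost is a short amendment to two sections. It adds no visits, scans or patients, because Section 3.1 already plans cycles 3 and 4 for stable 5-day patients and the calendar already schedules the scans.
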